9.9. Health Economics

The health outcome measures will be collected according to the Schedule of Activities (Section 2).

Migraine-Specific Quality of Life Questionnaire version 2.1: The Migraine-Specific Quality of Life Questionnaire version 2.1 (MSQ v2.1) is a self-administered health status instrument that was developed to address the physical and emotional impact on functioning that is of specific concern to individuals suffering from migraine headaches. The instrument consists of 14 items that address 3 domains: (1) Role Function-Restrictive; (2) Role Function-Preventive; and (3) Emotional Function (Jinghwan et al. 1998b). The restrictive domain specifically measures disability as related to the impact on performance of normal activities, with the preventive domain addressing complete functional impairment and the emotional domain assessing the feelings related to disabling monthly migraine headache days. Responses are given using a 6-point Likert-type scale, ranging from “none of the time” to “all of the time.” Raw scores for each domain are computed as a sum of item responses, with the collective sum providing a total raw score that is then converted to a 0 to 100 scale, with higher scores indicating a better health status, and a positive change in scores reflecting functional improvement (Jinghwan et al. 1998a; Marting et al. 2000). The instrument was designed with a 4-week recall period and is considered reliable, valid, and sensitive to change in functional impairment due to migraine (Jinghwan et al. 1998b; Bagley et al. 2012).

Six-item Headache Impact Test (HIT-6): HIT-6 is a tool used to measure the impact headaches have on patient’s ability to function on the job, at school, at home and in social situations. The HIT-6 consists of six items: pain, social functioning, role functioning, vitality, cognitive functioning, and psychological distress. The patient answers each question using one of the following 5 responses: “never,” “rarely,” “sometimes,” “very often,” or “always.” These responses are summed to produce a total HIT-6 score that ranges from 36 to 78, where a higher score indicates a greater impact of headache on the daily life of the respondent (Shin et al. 2008). A validation study showed that the HIT-6 is a reliable and valid tool for measuring the impact of headache on daily life in both episodic and chronic migraine sufferers (Yang et al. 2011).

10. Statistical Considerations

10.1. Sample Size Determination

The study will screen an estimated 110 potential patients to ensure randomization of approximately 60 migraine patients. Enrollment will be stratified by type of migraine, episodic versus chronic, and patients will be randomly assigned to either LY3451838 or placebo in a 1:1 allocation ratio within each stratum. Enrollment in the chronic migraine stratum will be capped so that no more than approximately 50% of the randomized population will be patients with chronic migraine.

The analysis will be conducted using all randomized patients, and it is assumed that approximately 2% of the patient population will dropout during the 28 days treatment period.

The study will be considered successful if there is at least a [REDACTED] CCI probability that the number of monthly migraine headache days with LY3451838 treatment is [REDACTED] CCI days less than the number of monthly migraine headache days with placebo treatment [REDACTED]

Enrolling approximately 60 patients who are stratified by type of migraine, episodic versus chronic, and randomly assigned to either LY3451838 or placebo in a 1:1 allocation ratio within each stratum will provide approximately [REDACTED] CCI

CCI

10.2. Populations for Analyses

For purposes of analysis, the following populations are defined:

Population	Description
Enrolled	All patients who sign informed consent
Randomized	All patients who are assigned a study treatment. Patients who had no post randomization efficacy measure for the parameter being analyzed will be excluded.
Safety	All randomized patients who take at least 1 dose of double-blind study treatment. Patients will be included in the treatment group they were randomized to. In the event of a treatment error, patients will be analyzed according to the treatment they actually received.

10.3. Statistical Analyses

10.3.1. General Statistical Considerations

Statistical analysis of this study will be the responsibility of Lilly or its designee. Details of statistical analysis methods will be described in the SAP.

Efficacy analyses will be conducted on the randomized set. Safety analyses will be conducted on the safety population. When mean change from baseline is assessed, the patient will be included in the analysis only if the patient has a baseline and a postbaseline measurement.

In general, for analyses of numeric outcome measures during the treatment phase, baseline value is defined as the last observation at or before Visit 3. Treatment effects will be evaluated based on a 2-sided significance level of 0.05. No adjustments for multiplicity will be applied to comparisons of baseline characteristics or safety parameters.

A Bayesian analysis will be performed for the primary efficacy endpoint, and the corresponding frequentist analyses will be conducted as a sensitivity analysis. All other statistical inference will be performed using frequentist methods.

For continuous variables, descriptive statistics will include the number of patients, mean, median, standard deviation, minimum, and maximum. Categorical variables will be summarized using the number and percentage of patients.

Any change to the data analysis methods described in the protocol will require a protocol amendment ONLY if it changes a principal feature of the protocol. Any other change to the data analysis methods described in the protocol, and the justification for making the change, will be described in the clinical study report. Additional exploratory analyses of the data will be conducted as deemed appropriate.

SAS® software version 9.4 or higher will be used to perform statistical analyses, unless otherwise specified.

10.3.2. Treatment Group Comparability

10.3.2.1. Patient Disposition

A detailed description of patient disposition will be provided at the end of the study. All patients who discontinue from the study will be identified, and the extent of their participation in the study will be summarized by treatment. If known, a reason for their discontinuation will be given.

10.3.2.2. Patient Characteristics

The following patient characteristics at baseline will be summarized by treatment.

- Demographic (age, sex, ethnic origin, height, weight, body mass index)
- Migraine and/or headache-related measures from the ePRO diary per 1-month baseline period

- Number of prior migraine preventive treatment failures from the list in Section 6.1 (Inclusion Criterion #6):
 - Failed 2 medication categories
 - Failed 3 medication categories
 - Failed 4 medication categories
- Medical history and pre-existing conditions

Medical history and pre-existing conditions will be summarized by preferred term within system organ class (SOC).

10.3.2.3. Concomitant Therapy

The proportion of patients who received concomitant medication and acute medications will be summarized.

10.3.2.4. Treatment Compliance

Any dose reduction, overdose, or dose delay will be summarized for all treated patients by cohort.

10.3.3. Efficacy Analyses

10.3.3.1. Primary Analyses

The primary analysis will be performed using an analysis of covariance (ANCOVA) model for the change from baseline in the monthly number of migraine headache days. The model will include randomized treatment and type of migraine as fixed effects and the baseline number of monthly migraine headache days as a covariate. The analysis will use a non-informative prior for the treatment effect. The treatment group means, treatment contrast, and their respective 95% credible regions as well as the success criterion will be based on the posterior treatment effect distributions.

10.3.3.2. Secondary Analyses

Frequentist analyses for change from baseline in the monthly number of migraine headache days and change from baseline in the monthly number of headache days will be performed using the ANCOVA model. Comparisons between the treatments in rate of responders will be conducted using Cochran Mantel Haenszel tests that are stratified by the type of migraine.

10.3.3.3. Exploratory Analyses

Details on exploratory analysis will be provided in the SAP.

10.3.4. Safety Analyses

The safety and tolerability of treatment will be assessed by summarizing the following:

- TEAEs
- SAEs
- AEs leading to discontinuation

- Potential hypersensitivity events
- AEs related to injection site reactions
- Vital signs
- Physical and neurological examinations
- ECGs
- Laboratory measurements
- CBB

The parameters will be listed, and summarized using standard descriptive statistics. Additional analysis will be performed as required.

10.3.6. Evaluation of Immunogenicity

The frequency and percentage of patients with preexisting ADA and with TE-ADA+ to LY3451838 may be tabulated.

Treatment-emergent ADAs are defined as those with a titer 2-fold (1 dilution) greater than the minimum required dilution if no ADAs were detected at baseline (treatment-induced ADA) or those with a 4-fold (2 dilutions) increase in titer compared to baseline if ADAs were detected at baseline (treatment-boosted ADA). For the TE-ADA+ patients the distribution of maximum titers may be described. The frequency of neutralizing antibodies may also be tabulated in TE ADA+ patients, when available.

The relationship between the presence of antibodies and the PK parameters and PD response including safety and efficacy to LY3451838 may be assessed.

10.3.7. Other Analyses

10.3.7.1. Health Economics

The change from baseline for the treatment phase for MSQ v2.1 and HIT-6 will be analyzed. In addition, categorical analyses will be performed. Additional details will be provided in the SAP.

10.3.7.2. Analysis of C-SSRS Data

Suicide-related thoughts and behaviors occurring during treatment will be summarized based on responses to the C-SSRS consistent with the C-SSRS Scoring and Data Analysis Guide.

Additional details will be provided in the SAP.

10.3.8. Interim Analyses

An interim analysis is planned when data from the majority of randomized patients have completed the 1-month treatment period. The interim efficacy results may be used for internal decision-making to trigger planning activities associated with the investigational product. No adjustment of Type I error will be performed as the study will not be stopped for efficacy, and no modification of Study LAJB is expected based on these interim results. The assessment would be conducted by a sponsor assessment committee with a limited number of preidentified team members who do not have direct site contact or data entry/validation responsibilities. Unblinding details will be specified in the unblinding plan section of the SAP or in a separate unblinding plan document. Information that may unblind the study during the analyses will not be reported to study sites or to the blinded study team until the study has been unblinded.

11. References

[ICHD-3] The International Classification of Headache Disorder, 3rd edition. *Cephalgia*. 2018;38(1):1-211.

Begasse de Dhaem OAJ, French J, Morrison C, et al. Migraine comorbidity and cognitive performance in patients with focal epilepsy. *Epilepsy Behav*. 2019;97:29-33.

Buse DC, Manack An, Fanning KM, et al. Chronic migraine prevalence, disability, and sociodemographic factors: results from the American Migraine Prevalence and Prevention Study. *Headache*. 2012;52(10):1456-70.

Cogstate resources page. Cogstate web site. Available at: <https://www.cogstate.com/clinical-trials/computerized-cognitive-assessment/featured-batteries/>. Accessed July 7, 2020.

Appendix 1. Abbreviations and Definitions

Term	Definition
ADA	anti-drug antibody
AE	adverse event: Any untoward medical occurrence in a patient or clinical investigation subject administered a pharmaceutical product that does not necessarily have a causal relationship with this treatment. An adverse event can therefore be any unfavorable and unintended sign (including an abnormal laboratory finding), symptom, or disease temporally associated with the use of a medicinal (investigational) product, whether or not related to the medicinal (investigational) product.
ALT	alanine aminotransferase
ALP	alkaline phosphatase
ANCOVA	analysis of covariance
AST	aspartate aminotransferase
AUC	area under concentration-time curve
blinding/masking	A double-blind study is one in which neither the [patient] nor any of the investigator or sponsor staff who are involved in the treatment or clinical evaluation of the patients are aware of the treatment received.
CAS	Cranial Autonomic Symptoms
CBB	Cogstate Brief Battery
CGRP	calcitonin gene-related peptide
C_{max}	maximum observed drug concentration
compliance	Adherence to all study-related, good clinical practice (GCP), and applicable regulatory requirements.
CRP	C-reactive protein
C-SSRS	Columbia Suicide Severity Rating Scale
CV	coefficient of variance
dBm	digital biomarker
ECG	electrocardiogram
EDC	electronic data capture system
enroll	The act of assigning a patient to a treatment. Patients who are enrolled in the study are those who have been assigned to a treatment.

enter	Patients entered into a study are those who sign the informed consent form directly or through their legally acceptable representatives.
ePRO	electronic patient-reported outcomes
ESR	erythrocyte sedimentation rate
GCP	good clinical practice
HIT-6	Headache Impact Test
HIV	human immunodeficiency virus
IB	Investigator's Brochure
ICF	informed consent form
ICH	International Council for Harmonisation
ICHD-3	International Classification of Headache Disorders version 3
Ig	immunoglobulins
IHS	International Headache Society
Informed consent	A process by which a patient voluntarily confirms his or her willingness to participate in a particular study, after having been informed of all aspects of the study that are relevant to the patient's decision to participate. Informed consent is documented by means of a written, signed and dated informed consent form.
IV	intravenous
IVRS/IWRS	interactive voice-response system/interactive web-response system
MOH	medication overuse headache
MSQ	Migraine Specific Quality of Life Questionnaire
NOAEL	no-observed-adverse-effect-level
PACAP	pituitary adenylate cyclase-activating peptide
PK/PD	pharmacokinetics/pharmacodynamics
QTc	corrected QT interval
SAE	serious adverse event
SAP	statistical analysis plan
SC	subcutaneous
screen	The act of determining if an individual meets minimum requirements to become part of a pool of potential candidates for participation in a clinical study.

SUSARs	suspected unexpected serious adverse reactions
TBL	total bilirubin
TE-ADA	treatment-emergent antidrug antibody
TEAE	Treatment-emergent adverse event: An untoward medical occurrence that emerges during a defined treatment period, having been absent pretreatment, or worsens relative to the pretreatment state, and does not necessarily have to have a causal relationship with this treatment.
ULN	upper limit of normal
VIP	Vasoactive intestinal peptide
WOCBP	Women of child-bearing potential

Appendix 2. Clinical Laboratory Tests

Clinical Laboratory Tests

Hematology

Hemoglobin
Hematocrit
Erythrocyte count (RBC)
Mean cell volume
Mean cell hemoglobin concentration
Leukocytes (WBC)
Neutrophils, segmented
Lymphocytes
Monocytes
Eosinophils
Basophils
Platelets
Erythrocyte sedimentation rate (ESR)

Urinalysis

Specific gravity
pH
Protein
Glucose
Ketones

Blood
Urine leukocyte esterase^a

Clinical Chemistry

Serum Concentrations of:
Sodium
Potassium
Total bilirubin
Direct bilirubin
Alkaline phosphatase
Alanine aminotransferase (ALT)
Aspartate aminotransferase (AST)
Blood urea nitrogen (BUN)
Creatinine
Uric acid
Calcium
Fasting Glucose
Glycosylated hemoglobin (HbA1c)
Albumin
Cholesterol
Creatine kinase (Total CK)
Estimated glomerular filtration rate (eGFR)^b
C-reactive protein (CRP)
Complement component 3 (C3)
Complement component 3a (C3a)
Complement component 4a (C4a)

Pregnancy Test (serum^c/urine^d/follicle-stimulating hormone^e)
Hepatitis B surface antigen^f
Hepatitis C antibody^f
Human immunodeficiency virus^f
Urine drug screen^f

Abbreviations: CKD = chronic kidney disease; EPI = epidemiology collaboration; RBC = red blood cells; WBC = white blood cells.

- ^a A positive urine leukocyte esterase result will require a follow-up sample with microscopic analysis and possibly a urine culture.
- ^b eGFR for serum creatinine calculated by the central laboratory using the CKD EPI method
- ^c To be performed for women of child-bearing potential at screening only.
- ^d In case of a positive result, the pregnancy must be confirmed by a serum test.
- ^e To be performed for women of non-child-bearing potential with 6-12 months of spontaneous amenorrhea at screening only.
- ^f To be performed at screening only.

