A Bayesian analysis for the primary endpoint will be performed using an analysis of covariance (ANCOVA). The ANCOVA model for the change from baseline in the monthly number of migraine headache days will include terms for treatment and type of migraine, and baseline number of migraine headache days as a covariate will be used.

Frequentist analyses for change from baseline in the monthly number of migraine headache days and change from baseline in the monthly number of headache days will be performed using the same ANCOVA model.

Comparisons between the treatments in rate of responders will be conducted using Cochran Mantel Haenszel tests that are stratified by the type of migraine.

For continuous variables, descriptive statistics will include the number of patients, mean, median, standard deviation, minimum, and maximum. Categorical variables will be summarized using the number and percentage of patients.

2. Schedule of Activities

Table LAJB 2.1 Schedule of Activities

	Screening	Baseline	Treatment Phase			Follow-up						ED ^b
(Target) Interval (days) since previous visit	-	-	30	15	15	15	15	15	15	30	30	
Allowable range (days) between visits	3-90	30-40 ^a										
Interval allowance (days)			+5	±3	±3	±3	±3	±3	±3	±3	±3	
Visit	1	2	3	4	5	6	7	8	9	10	11	
Month	-	-	0	.5	1	1.5	2	2.5	3	4	5	
Informed consent	X											
Demographics	X											
Physical examination ^c	X	X	P	X	X	X	X	X	X	X	X	
Neurological examination	X	X	P	X	X		X		X	X	X	
Height ^d and weight	X		P								X	X
Medical history ^e and concurrent conditions	X											
Vital signs ^f	X		P, 1 h	X	X	X	X	X	X	X	X	
12-lead ECG ^g	X	X	P	X	X		X		X		X	X
Serum pregnancy test (WOCBP only) or FSH	X											
Urine pregnancy test (WOCBP only) ^h		X	P		X		X		X	X	X	X
HIV, hepatitis B and C	X											
Hematology, chemistry ⁱ (include eGFR)	X	X	P	X	X	X	X	X	X	X	X	
Creatine kinase (Total CK)	X		P	X	X		X				X	X
HbA1c			P		X							
Urinalysis	X	X	P		X		X					
CCI			P	X	X							
ePRO and headache medication log training		X										
Inclusion and exclusion criteria	X	X	P									
ePRO daily patient diary entry		X	X	X	X	X	X	X	X	X		
Headache medication log		X	X	X	X	X	X	X	X	X		
CCI		X	X	X	X	X	X	X	X	X		
CCI		X	X	X	X	X	X	X	X	X		
Randomization			P									
Study drug administration			X									
MSQ v2.1			X		X		X		X		X	
HIT-6			X		X		X		X		X	

	Screening	Baseline	Treatment Phase			Follow-up						ED ^b
(Target) Interval (days) since previous visit	-	-	30	15	15	15	15	15	15	30	30	

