10. Women of child-bearing potential who are abstinent (if this is complete abstinence, as their preferred and usual lifestyle) or in a same sex relationship (as part of their preferred and usual lifestyle) must agree to either remain abstinent or agree to avoid sexual relationships with males. Periodic abstinence (eg, calendar, ovulation, symptothermal, post-ovulation methods), declaration of abstinence just for the duration of a trial, and withdrawal are not acceptable methods of contraception.
11. Women of child-bearing potential who are not abstinent, as defined above, must agree to use one highly effective method (less than 1% failure rate) of contraception, or a combination of two effective methods of contraception for the entirety of the study as well as 5 months after study drug administration.

Highly effective methods of contraception include combination oral contraceptives, implanted contraceptives or intrauterine device. Effective methods of contraception include male or female condoms with spermicide, and diaphragms with spermicide or cervical sponges. The patient may choose to use a double barrier method of contraception. Barrier protection methods without concomitant use of a spermicide are not a reliable or acceptable method. Thus, each barrier method must include use of a spermicide. It should be noted that the use of male and female condoms as a double barrier method is not considered acceptable due to the high failure rate when these methods are combined.

12. Women not of child-bearing potential may participate and include those who are:
 - a. infertile due to surgical sterilization (hysterectomy, bilateral oophorectomy, or tubal ligation), congenital anomaly such as mullerian agenesis; or
 - b. post-menopausal – defined as either
 - i. a woman at least 40 years of age with an intact uterus, not on hormone therapy, who has cessation of menses for at least 1 year without an alternative medical cause, and a follicle-stimulating hormone >40 mIU/mL; or
 - ii. a woman 55 or older not on hormone therapy, who has had at least 12 months of spontaneous amenorrhea; or
 - iii. a woman at least 55 years of age with a diagnosis of menopause prior to starting hormone replacement therapy.
13. Agree not to voluntarily change habits or routines that represent a potential migraine trigger factor or protective measure including, but not limited to, substantial diet changes, physical exercise, or sleep habits.

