9.4.4. Laboratory Tests

For each patient, laboratory tests detailed in ([Appendix 2](#)) should be conducted according to the Schedule of Activities (Section 2).

With the exception of laboratory test results that may unblind the study, Lilly or its designee will provide the investigator with the results of laboratory tests analyzed by a central vendor. Note that any result that may unblind a site would not be shared.

Any clinically significant findings from laboratory tests that result in a diagnosis should be reported to Lilly, or its designee, as an AE via EDC.

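### Appendix 2 sends women with 6 to 12 months of amenorrhea for FSH and labels them non-child-bearing, but the only criterion that uses FSH starts at 1 year, so the two groups meet only at 12 months

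*Protocol*

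**What the plan says.** Three places in the current protocol text bear on who has FSH measured, and a fourth links them.

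- **Appendix 2, footnote e**, attached to the FSH entry: "To be performed for women of non-child-bearing potential with 6-12 months of spontaneous amenorrhea at screening only".
- **Section 6.1, criterion 12.b.i**: a woman of at least 40 with an intact uterus and not on hormone therapy counts as post-menopausal if she is one "who has cessation of menses for at least 1 year without an alternative medical cause, and a follicle-stimulating hormone >40 mIU/mL".
- **Section 2, Schedule of Activities**: the row "Serum pregnancy test (WOCBP only) or FSH" is marked at screening. It gives no amenorrhea duration and no rule for which women get FSH.
- **Section 9.4.4** joins the two lists. It opens "For each patient, laboratory tests detailed in" Appendix 2 and has those tests done at the times in the Schedule.

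The other routes in criterion 12 need no FSH value. Route 12.a covers surgical sterilization and congenital anomaly. Route 12.b.ii covers "a woman 55 or older not on hormone therapy, who has had at least 12 months of spontaneous amenorrhea". Route 12.b.iii covers "a woman at least 55 years of age with a diagnosis of menopause prior to starting hormone replacement therapy".

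**The concern.** FSH has one eligibility use in this protocol: to complete the post-menopausal classification under 12.b.i. The women sent for the test should be those whose classification depends on it. Footnote e names a nearly separate group. It also describes that group as already non-child-bearing, which takes as given the status that the FSH result is meant to help establish.

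The status matters because it controls safeguards. Criterion 9 asks for a negative serum test at screening and a negative urine test within 24 hours before exposure, but only from women of child-bearing potential. The pregnancy-test rows in the Schedule carry the same restriction. Criteria 10 and 11 set abstinence and contraception requirements for women of child-bearing potential, and the contraception under criterion 11 extends to 5 months after dosing. Section 6.3 requires no contraception from non-child-bearing women unless local rules do. Pregnancy is an exclusion (criterion 33). A wrong label at screening therefore carries through to exposure.

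**Working it through.** The plan states no figure to reproduce here. The check compares two duration ranges and then reads off what each passage does with each group.

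**Inputs**
- Range named for FSH (Appendix 2, footnote e): 6 to 12 months.
- Range in which FSH is needed (criterion 12.b.i): at least 1 year, that is, 12 months or more.
- Range for 12.b.ii: at least 12 months, age 55 or older, no FSH.
- Routes 12.a and 12.b.iii: no amenorrhea duration and no FSH.

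**Step 1: overlap.** The range from 6 to 12 months and the range from 12 months upward share a single point, 12 months.

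**Step 2: who depends on 12.b.i.** A woman of 55 or older, not on hormone therapy, with at least 12 months of amenorrhea already qualifies under 12.b.ii. Women who meet 12.a or 12.b.iii need no FSH either. In practice, then, 12.b.i decides the status of women aged 40 to 54 with an intact uterus and not on hormone therapy who do not qualify by another route.

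**Step 3: side by side, for women who do not qualify under 12.a or 12.b.iii.**

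| Amenorrhea | Footnote e | Criterion 12.b |
|---|---|---|
| 6 to under 12 months | Named for FSH; labelled non-child-bearing | Too short for 12.b.i and 12.b.ii, whatever the FSH value |
| Exactly 12 months | Named for FSH | Long enough for 12.b.i and 12.b.ii |
| More than 12 months | Not named for FSH | Ages 40 to 54: FSH needed under 12.b.i. Age 55 or older: 12.b.ii, no FSH |

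**Step 4: consequence of each mismatch.**
- *More than 12 months, dependent on 12.b.i.* Appendix 2 does not call for the test. Criterion 12.b.i joins duration and FSH with an *and*, so a woman with no result does not meet it. She stays under the child-bearing rules and is tested and counselled accordingly.
- *6 to under 12 months.* She is tested, but the result cannot bring her under 12.b.i. If the site acts on the footnote's label, the pregnancy tests and contraception rules do not apply to her. The Schedule row offers a serum pregnancy test *or* FSH, so it does not prevent FSH from being done in place of the pregnancy test.

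**Step 5: does the Schedule settle it?** In part. It places FSH at screening with no duration limit, so a site could order the test for a woman with more than 12 months of amenorrhea. It does not say which women get FSH. Footnote e is the only text that does.

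**The case against.** The strongest reply is that the eligibility criteria govern and fail safe. Three parts of it stand.

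- A reader might infer that women with more than 1 year of amenorrhea could be classed as non-child-bearing with no FSH result and so skip pregnancy testing. The documents do not support this. Criterion 12.b.i requires the result, its absence leaves the woman under the child-bearing rules, and Section 6 does not permit waivers of enrollment criteria.
- A reader might infer that the protocol nowhere lists FSH for the women who need it. That is true of Appendix 2 only. The Schedule lists FSH at screening without a duration limit.
- A reader might infer that no woman with 6 to 12 months of amenorrhea can be non-child-bearing under criterion 12. That is too strong. Routes 12.a and 12.b.iii do not depend on duration, so such a woman may qualify by another route. What holds is that the duration alone does not qualify her under 12.b.i or 12.b.ii.

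The reply does not remove the contradiction. No passage ranks criterion 12 above Appendix 2, and Section 9.4.4 sends sites to Appendix 2 for the detail of the tests. The Schedule's silence on who gets FSH also leaves the label in footnote e uncorrected.

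**Conclusion.** The inconsistency is real, lies in current text, and is not produced by redaction or by the amendment summary. The group named for FSH and the group whose status depends on FSH meet only at 12 months. The more consequential half is the label on women with 6 to under 12 months, because a site that relies on it could drop pregnancy tests and contraception for women whom criterion 12 does not class as post-menopausal on that basis. The other half, the missing call for FSH beyond 12 months, leads to more testing rather than less.

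The size in patients cannot be stated. The documents give no distribution of age, sex or menopausal status, either for the estimated 110 to be screened or for the approximately 60 to be randomized. The point is minor for the trial as a whole: no endpoint, sample size, analysis population or estimate changes. The safety consequence rests on one assumption, that a site acts on the footnote's label rather than checking it against criterion 12.

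**What to change.** Reconcile Appendix 2 footnote e, criterion 12 in Section 6.1 and the FSH row of the Schedule of Activities, so that the women sent for FSH, and the child-bearing label attached to them, agree with the eligibility criterion that depends on the result. The Schedule row should state, or point to, the rule for who gets FSH and who gets the serum pregnancy test. Which amenorrhea duration and which classification rule are right is a clinical decision for the sponsor, and this review does not propose one.

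The cost is a short text correction. FSH is already a screening test, so no new visit or assay type is needed. The number of FSH tests could change, depending on the rule the sponsor adopts.
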